### 2.1. Multiplicity Adjustment

Analyses of efficacy endpoints will not be subject to any multiplicity adjustment.

### 3. ANALYSIS SETS

Analysis Set	Definition / Criteria	Analyses Evaluated
Screened	
 
• All participants who were screened for eligibility.
 
	
 
• Study Population
 

Enrolled	
 
• All participants who passed screening and entered the study
 
• Note: screening failures (who never passed screening even if rescreened) and participants screened but never enrolled into the study are excluded from the Enrolled population as they did not enter the study
 
	
 
• Study Population
 

Safety	
 
• All participants who received at least one dose of study treatment
 
	
 
• Safety
 
• Virology
 

ITT	
 
• All participants who received at least one dose of study treatment
 
• Note: As no randomization took place on this study, Safety and ITT analysis set will contain the same set of participants.
 
	
 
• Efficacy
 
• Virology
 

Pharmacokinetic (PK)	
 
• All participants in the Safety population who received an active study treatment and had at least 1 non-missing PK assessment (Non-quantifiable [NQ] values will be considered as non-missing values)
 
• Note: PK samples that may be affected by protocol deviations will be reviewed by the study team to determine whether or not the sample will be excluded
 
	
 
• PK
 

Defined Analysis Data Sets	Description
Analysis set for primary estimand	All Intent to Treat Participants including all observations on and off treatment.
Analysis set for secondary estimands	All Intent to Treat Participants including all observations on and off treatment.

### 4. STATISTICAL ANALYSES

#### 4.1. General Considerations

##### 4.1.1. General Methodology

Participants who prematurely withdrew from study will not be replaced.

Confidence intervals will use 95% confidence levels unless otherwise specified.

Unless otherwise specified, continuous data will be summarized using descriptive statistics: n, mean, standard deviation (std), median, minimum and maximum. Categorical data will be summarized as the number and percentage of participants in each category.

HBV DNA (as appropriate), HBV RNA, HBcrAg and HBsAg levels that are below the LLOQ will be imputed for summaries of actual values and change from baseline.

The numeric values for HBV DNA <LLOQ (LLOQ=20 IU/mL) will be imputed as 19.9. The numeric values for HBsAg <LLOQ (LLOQ=0.05 IU/mL) will be imputed as 0.04. For HBV RNA and HBcrAg, values <LLOQ are imputed based on the number of significant digits, similar to other lab parameters. For further handling of significant digits, please see OPS.

HBV DNA (IU/mL) and HBV RNA (copies/mL) levels that are “TND” will be imputed as 1. HBcrAg (Log10 U/mL) values that are “TND” will be imputed as 0.

#### **4.1.2. Baseline Definition**

For all endpoints (except as noted in baseline definitions) the baseline value will be the latest pre-dose assessment with a non-missing value, including those from unscheduled visits. If time is not collected, Day 1 assessments are assumed to be taken prior to first dose and used as baseline. If there are multiple assessments collected at the same scheduled time, the average of these assessments will be used as the baseline.

Unless otherwise stated, if baseline data is missing no derivation will be performed and baseline will be set to missing.

Baseline of eGFR and serum creatinine is defined as the mean of all pre-dose values, from screening to Day 1 pre-dose assessment.

### **4.2. Primary Endpoint(s) Analyses**

The primary analysis will be conducted once the last participant has completed the Week 36 visit (completed 24-weeks of follow-up period) and database lock has been achieved. The primary efficacy endpoint is achieving serum HBsAg level <LLOQ at any time point during 12-weeks (including Week 12) of GSK3228836 treatment. HBsAg at any time point up to and including Week 12 will be used to assess the primary endpoint.

#### **4.2.1. Definition of estimands**

The Primary Estimand supporting the primary objective of the study is defined as:

- **Population:** Participants with CHB who receive at least 1 dose of IP
- **Treatment:** 300 mg GSK3228836 for 12 weeks (also on stable nucleos(t)ide therapy)

- **Variable:** Achieving serum HBsAg level <LLOQ at any time point up to and including Week 12 without the use of PEG-interferon or other immunomodulator therapies
- **Population-level summary:** Percent of participants that achieve serum HBsAg level <LLOQ at any time point up to and including Week 12
- **Intercurrent events:** Discontinuation of, interruption of, and adherence to IP will be ignored (treatment policy).

The primary estimand is the percentage of participants with CHB receiving 300 mg GSK3228836 for 12 weeks (with at least one dose of IP) who achieve serum HBsAg level <LLOQ at any time point up to and including Week 12, without the use of PEG-interferon or other immunomodulator therapies, regardless of completing IP, interruptions in IP or adherence to IP. If PEG-interferon or other immunomodulator therapies are used, then the participant's primary outcome will be treated as a non-responder.

#### 4.2.2. Main analytical approach

The primary assessments of interest are the point estimate and the 95% credible interval of achieving serum HBsAg level <LLOQ up to and including Week 12.

In addition, posterior probability that the true virologic response rate is greater than 50% will be provided. A Bayesian approach will be used to estimate the posterior probability. A weakly informative prior beta (0.5, 0.5) will be used.

Let Y be the number of responders from N participants,

$Y \sim \text{Binomial}(N, p)$

Where p is virologic response rate.

The posterior distribution for p is  $P(p|y, N) \sim \text{Beta}(y + 0.5, N - y + 0.5)$

The posterior probability that the true rate of participants achieving LLOQ by Week 12 being greater than 50% will be calculated from the posterior distribution.

The following will be presented:

Model Results Presentation

• Number and percent of participants achieving serum HBsAg level <LLOQ by Week 12.

• Posterior 95% credible interval (Highest Density Interval, HDI) of participants achieving serum HBsAg level <LLOQ by Week 12.

• Posterior probability that the true rate of participants achieving LLOQ by Week 12 being greater than 50%

#### 4.2.2.1. Intercurrent Events and Missing Data

The intercurrent event of discontinuation of, interruption of, and adherence to IP will be ignored (treatment policy).

A participant's response (Responder or Non-responder) is determined as follows:

- If participant took rescue medication of PEG-interferon or other immunomodulator therapies during 12 week treatment period or during 24 week follow-up period then participant is Non-Responder
- Else if participant reached HBsAg < LLOQ at any point during the 12 week treatment period then participant is a Responder.
- Otherwise participant is Non-Responder.

If a participant has missing data during the 12 week treatment period, but still falls under the responder then they will still be considered a responder.

HBsAg values at any timepoint up to and including Week 12 are considered, including Unscheduled visits. See Section [6.2.5](#) for details on upper bound of analysis date.

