4. STUDY DESIGN

4.1. Overall Design

This study is a Phase IIa, multi-centre open label exploratory study of the therapeutic mechanism of GSK3228836 in participants with HBeAg-negative CHB on stable nucleos(t)ide therapy using repeat fine needle aspirations of the liver for intrahepatic immunophenotyping (see Section 1.2).

The study consists of a single treatment arm:

1. 300 mg GSK3228836 for 12 weeks (loading schedule on Day 4 and Day 11). Participants will continue to receive their stable nucleos(t)ide therapy.

After the 12 weeks of dosing with GSK3228836, there will be a post-treatment follow-up period of 24 weeks. An Independent Data Monitoring Committee (IDMC) will review the data (see Section 10.1.5).

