6.8.2. Prohibited Medications and Non-Drug Therapies

The following concomitant medications are not permitted during the study:

- PEG-interferon or other immunomodulating therapies
- Immunosuppressing drug (e.g., prednisone) use >2 weeks duration from 3 months prior to Screening through the final Follow-up visit (see Section 5.2), unless required for safety
- Prior treatment with any oligonucleotide or small interfering RNA (siRNA) within 12 months prior to the first dosing through the final Follow-up visit

- Creatine-containing gym supplements
- Anti-coagulation therapies (for example warfarin, Factor Xa inhibitors or anti-platelet agents like clopidogrel). Note: occasional use of aspirin is permitted, please consult the medical monitor if needed.

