9.4.2. Primary Endpoint(s)

The primary analysis will be conducted once the last participant has completed the Week 36 visit (completed 24-weeks of follow-up period) and database lock has been

achieved. The primary efficacy endpoint is achieving serum HBsAg level <LLOQ at any time point during 12-weeks (including Week 12) of GSK3228836 treatment.

The Primary Estimand supporting the primary objective of the study is defined as:

- Population: Participants with CHB who receive at least 1 dose of IP
- Treatment: 300 mg GSK3228836 for 12 weeks (also on stable nucleos(t)ide therapy)
- Variable: Achieving serum HBsAg level <LLOQ at any time point up to and including Week 12 without the use of PEG-interferon or other immunomodulator therapies
- Population-level summary: Percent of participants that achieve serum HBsAg level <LLOQ at any time point up to and including Week 12
- Intercurrent events: Discontinuation of, interruption of, and adherence to IP will be ignored (treatment policy).

The primary estimand is the percentage of participants with CHB receiving 300 mg GSK3228836 for 12 weeks (with at least one dose of IP) who achieve serum HBsAg level <LLOQ at any time point up to and including Week 12, without the use of PEG-interferon or other immunomodulator therapies, regardless of completing IP, interruptions in IP or adherence to IP. If PEG-interferon or other immunomodulator therapies are used, then the participant's primary outcome will be treated as a failure.

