#### 6.2.5. Assessment Windows for Analyses and Multiple Measurements at One Analysis Timepoint

The primary endpoint is defined as “Achieving serum HBsAg level <LLOQ at any time point up to and including Week 12 without the use of PEG-interferon or other immunomodulator therapies”. No analysis window will be assigned and all values up to Week 12, including unscheduled visit results, will be considered. The upper bound of the analysis date is defined as:

Target day of the Week 12 visit (78) + 3 days

Note: 3 days as allowed for the Week 12 dosing.

For secondary endpoints:

- sustained Virologic Response (HBsAg <LLOQ and HBV DNA <LLOQ)
- sustained HBsAg Response (HBsAg <LLOQ) for 24 weeks

after the planned end of GSK3228836 treatment (all values including unscheduled visit results will be considered):

	Parameter (if applicable)	Target Study Day	Analysis Window		Analysis Timepoint	Protocol Visit
			Beginning Timepoint	Ending Timepoint		
Efficacy	HBsAg and HBV DNA; or HBsAg	78	64	98	End of '836 Treatment – Planned	Week 12
		134	99	154	Post '836 treatment Week 8 – Planned	Week 20
		190	155	210	Post '836 treatment Week 16 – Planned	Week 28
		246	211	266	Post '836 treatment Week 24 – Planned	Week 36

For secondary endpoints:

- sustained Virologic Response(HBsAg <LLOQ and HBV DNA<LLOQ)
- sustained HBsAg Response(HBsAg <LLOQ) 24 weeks

after the actual end of GSK3228836 treatment (all values including unscheduled visit results will be considered):

	Parameter (if applicable)	Target Study Day	Analysis Window		Analysis Timepoint	Protocol Visit
			Beginning Timepoint	Ending Timepoint		
Efficacy	HBsAg and HBV DNA; or HBsAg	X = Target study day of the last treatment dose	Max (X-14, 1)	X+20	End of '836 Treatment - Actual	-
		X + 56	X+21	X + 76	Post '836 treatment Week 8 - Actual	-
		X + 112	X+ 77	X + 132	Post '836 treatment	-

	Parameter (if applicable)	Target Study Day	Analysis Window		Analysis Timepoint	Protocol Visit
			Beginning Timepoint	Ending Timepoint		
					Week 16 - Actual	
		X + 168	X + 133	X + 188	Post '836 treatment Week 24 - Actual	-

1. For example, if the subject received the last treatment dosing at the W2/D8 visit, then the target day is 8; if the subject received the last treatment dosing at the W2/D11 visit (loading schedule), then the target day is 11; if the subject received the last treatment dosing at the W9/D57 visit, then the target day is 57.

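### The primary responder rule in SAP 4.2.2.1 counts immunomodulator use through follow-up, so use after Day 81 can undo a response already reached by Week 12

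*SAP*

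**What the plan says.** SAP 4.2.1 defines the primary variable as "Achieving serum HBsAg level <LLOQ at any time point up to and including Week 12 without the use of PEG-interferon or other immunomodulator therapies". Protocol 9.4.2 describes the same participants as those "who achieve serum HBsAg level <LLOQ at any time point up to and including Week 12, without the use of PEG-interferon or other immunomodulator therapies". SAP 6.2.5 sets the last date for HBsAg values at "Target day of the Week 12 visit (78) + 3 days", that is Day 81. The results listed in SAP 4.2.2 are all labelled as achieved by Week 12.

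SAP 4.2.2.1 turns this into an ordered rule. Step 1 makes anyone who took PEG-interferon or another immunomodulator "during 12 week treatment period or during 24 week follow-up period then participant is Non-Responder". HBsAg is read only in step 2: "Else if participant reached HBsAg < LLOQ at any point during the 12 week treatment period then participant is a Responder". Everyone else is a Non-Responder.

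Three other statements bear on the point:

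- Protocol 9.4.2 closes the estimand with "If PEG-interferon or other immunomodulator therapies are used, then the participant's primary outcome will be treated as a failure". SAP 4.2.1 has the equivalent sentence with non-responder in place of failure. Neither gives a time limit.
- Protocol 4.1 states that after dosing "there will be a post-treatment follow-up period of 24 weeks".
- Protocol 6.8.2 lists "PEG-interferon or other immunomodulating therapies" among the medications not permitted during the study.

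**The concern.** Step 1 is evaluated before any HBsAg result, and it looks well past the point at which the endpoint is decided. Take a participant who is below LLOQ at Week 8 with no immunomodulator, loses the response off treatment, and takes PEG-interferon at Week 30. Every HBsAg value that counts for the primary endpoint was measured by Day 81. Therapy started later cannot have influenced those values, so counting it removes no confounding. The participant is still scored a Non-Responder.

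What is at stake is the meaning of the primary rate. With this rule it can combine HBsAg loss on treatment with what happens to the participant off treatment. It would also depend on how long each participant is observed: a responder who withdraws at Week 14 has less time in which to be rescored than one who stays to Week 36. Any such rescoring moves the rate one way only, downward.

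**Working it through.** **1. Time windows side by side**

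| Element | Place | Ends at |
|---|---|---|
| Endpoint variable | Protocol 9.4.2, SAP 4.2.1 | Week 12 |
| HBsAg data | SAP 6.2.5 | Day 78 + 3 = Day 81 |
| Reported results | SAP 4.2.2 | Week 12 |
| Closing sentence on use | Protocol 9.4.2, SAP 4.2.1 | not stated |
| Step 1 of the responder rule | SAP 4.2.2.1 | end of follow-up, Week 36 (Day 246) |

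From the Week 12 visit to the last visit is 246 − 78 = 168 days, or 24 weeks. Counted from an earlier response the gap is longer: Day 29 to Day 246 is 217 days, or 31 weeks.

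The SAP does vary this window by endpoint. In SAP 4.3.1.1 the planned-end rule counts use in both periods, while the actual-end rule counts follow-up only. Those endpoints are about follow-up, so a follow-up condition belongs there.

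**2. The plan's own figures**

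Inputs: N = 20, prior Beta(0.5, 0.5), and the criterion P(p > 50%) > 75% (SAP 4.2.2 and 5). The posterior is Beta(y + 0.5, N − y + 0.5).

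- The smallest y that meets the criterion is 12, with posterior probability 0.814. This agrees with the stated minimum of 12.
- P(X ≥ 12) for a Binomial(20, p) is 0.596 at p = 0.60 and 0.887 at p = 0.70. The plan states 60% and 89%, so both reproduce.

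**3. Effect of rescoring one responder**

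One participant is 1/20 = 5 percentage points.

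| Responders | P(p > 50%) before | P(p > 50%) after | Still above 75%? |
|---|---|---|---|
| 12 to 11 | 0.814 | 0.672 | no |
| 13 to 12 | 0.911 | 0.814 | yes |
| 14 to 13 | 0.965 | 0.911 | yes |

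For 12 to 11, the 95% highest-density interval moves from 39%–80% to 34%–75%.

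**4. Effect on the operating characteristics**

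The documents give no rate of use. Assume that a share q of Week 12 responders takes such therapy only in follow-up. The scored rate is then p(1 − q), and the chance of meeting the criterion is P(X ≥ 12) at that rate.

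| q (assumed) | True rate 60%: scored rate, chance | True rate 70%: scored rate, chance |
|---|---|---|
| 0% | 60.0%, 59.6% | 70.0%, 88.7% |
| 2% | 58.8%, 55.2% | 68.6%, 85.7% |
| 5% | 57.0%, 48.6% | 66.5%, 80.5% |
| 10% | 54.0%, 37.9% | 63.0%, 70.0% |
| 20% | 48.0%, 19.8% | 56.0%, 45.0% |

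**The case against.** The best defence is the closing sentence of the estimand. It treats use as failure without saying when, and the primary analysis runs only after the last Week 36 visit. SAP 4.2.2.1 can therefore be applied as written and is a permissible reading. This stands: a reader might infer that the SAP contradicts the protocol, and the documents do not support that.

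The trigger is also a prohibited treatment. A reader might infer that the primary rate is biased downward as a matter of fact. It is not, unless a Week 12 responder later takes one of these therapies. The list of qualifying terms is in the Output and Programming Specification, which is not available here.

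The 75% figure appears only in the sample-size sections. SAP 2 specifies estimation with no hypothesis test, and SAP 4.2.2 attaches no pass or fail rule to the posterior probability. The step from 12 to 11 is the one count at which a single participant crosses 75%.

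It is also tempting to say that the rule mislabels participants in the mechanistic comparison. That cannot be verified. The exploratory analyses are redacted, and the visible biomarker text in SAP 5 groups participants by whether they achieved HBsAg below LLOQ, without reference to the SAP 4.2.2.1 flag.

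Finally, the secondary summary of HBsAg below LLOQ over time discards data only from first use onward (Protocol 9.4.4), so on-treatment loss remains visible there. That softens the problem but does not repair the primary rate, and the two displays could disagree about the same participant.

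**Conclusion.** The point holds as a mismatch of time windows. The variable, the data cut-off and the reported results stop at Week 12, while the first scoring step runs to Week 36 and overrides the result. The underlying cause is an estimand sentence that does not say when use counts.

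The size is conditional: zero if no Week 12 responder uses these therapies in follow-up, and otherwise 5 points per participant at N = 20, always downward. The values of q above are assumptions that show a range and are not forecasts. The correction is still worth making before database lock, because it concerns the derivation of the primary endpoint and one participant can visibly shift the result in a study of this size.

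**What to change.** - In the first bullet of SAP 4.2.2.1, delete the reference to the 24-week follow-up. Count as Non-Responder anyone with any use on or before Day 81, whatever its order relative to the first HBsAg below LLOQ. A condition that use must precede that first value should not be added, because it would conflict with the closing estimand sentence, which exempts no use on grounds of order.
- State the limit as a study day. SAP 6.2.2 ends the on-treatment period the day before Off Treatment Day 1, which for a last dose on Day 78 is 78 + 7 − 1 = Day 84, so naming the treatment period alone could be read differently from Day 81.
- Add the same limit to the closing sentence of SAP 4.2.1, and list the change from Protocol 9.4.2 in SAP 4.8.
- Leave the follow-up condition in SAP 4.3.1.1 and 4.3.1.2.
- If the Week 36 window is intended, say so in the estimand and report the Day 81 version as a sensitivity analysis.

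The cost is a few lines of SAP text, one entry in SAP 4.8 and one programming condition. No new data are needed.

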### 4.3. Secondary Endpoint(s) Analyses

#### 4.3.1. Key secondary endpoint(s)

##### 4.3.1.1. Sustainability of Serum HBsAg loss

###### *Definition of estimands*

Estimands supporting the secondary objective of assessing sustainability of serum HBsAg loss by GSK3228836 for up to 24 weeks off-treatment are defined as follows:

- The group of estimands supporting this objective in participants with CHB receiving 300 mg GSK3228836 for 12 weeks (with at least one dose of IP) is the percentage of participants for each variable regardless of completing IP, interruptions in IP or adherence to IP, without the use of PEG-interferon or other immunomodulator therapies. If PEG-interferon or other immunomodulator therapies are used then the participant's outcome will be treated as a non-responder.
- **Variables:**
  - Sustained HBsAg Response (HBsAg < LLOQ) for 24 weeks after the planned end of GSK3228836 treatment without the use of PEG-interferon or other immunomodulator therapies
    - HBsAg from Week 13 to Week 36 will be used to assess sustained HBsAg response after the planned end of GSK3228836 treatment.

- Sustained HBsAg Response (HBsAg <LLOQ) for 24 weeks after the actual end of GSK3228836 treatment without the use of PEG-interferon or other immunomodulator therapies
  - HBsAg for 24 weeks after end of actual treatment will also be used to assess sustained HBsAg response after the actual end of GSK3228836 treatment.
- **Population Summary:** percentage of participants for each variable.

### ***Main analytical approach***

Percentages will be summarised and presented for:

- Sustainability of Serum HBsAg loss

Analysis windows for the post GSK3228836 treatment assessments are defined in Section [6.2.5](#).

If all analysis windows have non-missing response information, a participant's response (Responder or Non-responder) for sustained HBsAg response after the planned end of GSK3228836 treatment is determined as follows:

- If participant took PEG-interferon or other immunomodulator therapies during 12 week treatment period or 24 week follow-up period then participant is Non-Responder
- Else if participant had sustained HBsAg response (HBsAg <LLOQ) for 24 weeks after planned end of GSK3228836 treatment then participant is a Responder.
- Otherwise participant is Non-Responder.

If all analysis windows have non-missing response information, a participant's response (Responder or Non-responder) for sustained HBsAg response after the actual end of GSK3228836 treatment is determined as follows:

- If participant took PEG-interferon or other immunomodulator therapies during 24 week follow-up period then participant is Non-Responder
- Else if participant had sustained HBsAg response (HBsAg <LLOQ) for 24 weeks after actual end of GSK3228836 treatment then participant is a Responder.
- Otherwise participant is Non-Responder.

For participants where sustained HBsAg response in the absence of PEG-interferon or other immunomodulator therapies cannot be ascertained due to missing data (withdrawal from the study or missing due to other reasons), the participant will be assumed not to have achieved SVR (non-responder imputation).

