9.4.4. Secondary Endpoint(s)

Estimands supporting the secondary objective of assessing sustainability of serum HBsAg loss by GSK3228836 for up to 24 weeks off-treatment are defined as follows:

- The group of estimands supporting this objective in participants with CHB receiving 300 mg GSK3228836 for 12 weeks (with at least one dose of IP) is the percentage of participants for each variable regardless of completing IP, interruptions in IP or adherence to IP, without the use of PEG-interferon or other immunomodulator therapies. If PEG-interferon or other immunomodulator therapies are used then the participant's outcome will be treated as a failure.
- Variables:
 - Sustained HBsAg Response (HBsAg <LLOQ) for 24 weeks after the planned end of GSK3228836 treatment without the use of PEG-interferon or other immunomodulator therapies
 - HBsAg from Week 13 to Week 36 will be used to assess sustained HBsAg response after the planned end of GSK3228836 treatment.
 - Sustained HBsAg Response (HBsAg <LLOQ) for 24 weeks after the actual end of GSK3228836 treatment without the use of PEG-interferon or other immunomodulator therapies
 - HBsAg for 24 weeks after end of actual treatment will also be used to assess sustained HBsAg response after the actual end of GSK3228836 treatment.
- Population Summary: percentage of participants for each variable.
- Analysis windows for the post GSK3228836 treatment assessments will be defined in the analysis plan.

Estimands supporting the secondary objective of assessing sustainability of serum HBsAg and HBV DNA (Sustained Virologic Response) loss by GSK3228836 for up to 24 weeks off treatment are defined as follows:

- The group of estimands supporting this objective in participants with CHB receiving 300 mg GSK3228836 for 12 weeks (with at least one dose of IP) is the percentage of participants for each variable regardless of completing IP, interruptions in IP or adherence to IP, without the use of PEG-interferon or other immunomodulator therapies. If PEG-interferon or other immunomodulator therapies are used then the participant's outcome will be treated as a failure.
- Variables:
 - Sustained Virologic Response (HBsAg <LLOQ and HBV DNA <LLOQ) for 24 weeks after the planned end of GSK3228836 treatment

- HBsAg and HBV DNA from Week 13 to Week 36 will be used to assess sustained virologic response after the planned end of GSK3228836 treatment without the use of PEG-interferon or other immunomodulator therapies.

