**Table 1 Changes to Protocol Defined Analysis Plan**

Protocol Defined Analysis	SAP Defined Analysis	Rationale for Changes
Section 4.3.1.3, single table presented for:  Time to Event Variable • Time to Maximum ALT (ALT must be greater than 3xULN) during 36 weeks of	Now presenting 4 tables instead of one: 

Summary of Time to First Occurrence of Maximum ALT

	

At the time of writing the protocol, it was expected that only one peak in ALT would be seen. We have since seen on other studies, that more than one peak can occur.

Protocol Defined Analysis	SAP Defined Analysis	Rationale for Changes
treatment + follow up Population summary: Turnbull estimate for median Time to Maximum ALT (>3xULN)	
 
Summary of Time to First Occurrence of Maximum ALT during 12 week treatment period
 
Summary of Time to First Occurrence of Maximum ALT after GSK3228836 treatment
 
Summary of Time to Maximum ALT
 
	
 
The first analysis, is the analysis which was originally intended for the study looking at the first peak.
 
The other analyses reflect our newly updated learning for ALT, since the time of writing the protocol.
 

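### The SAP rule for sustained HBsAg response after actual end of treatment ignores immunomodulator use during treatment, against its own estimand, protocol 9.4.4 and the three parallel rules

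*SAP*

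**What the plan says.** SAP 4.3.1.1 and 4.3.1.2 define four sustained-response variables: HBsAg response and SVR (HBsAg and HBV DNA), each counted from the planned and from the actual end of treatment. Each has a stepwise responder rule whose first step deals with PEG-interferon and other immunomodulators.

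- HBsAg, actual end (4.3.1.1): "If participant took PEG-interferon or other immunomodulator therapies during 24 week follow-up period then participant is Non-Responder".
- HBsAg, planned end (4.3.1.1), and SVR, planned and actual end (4.3.1.2), all three in the same words: "If participant took PEG-interferon or other immunomodulator therapies during 12 week treatment period or 24 week follow-up period then participant is Non-Responder".

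The estimand in 4.3.1.1, which governs both HBsAg variables, says: "If PEG-interferon or other immunomodulator therapies are used then the participant's outcome will be treated as a non-responder". Protocol 9.4.4 says: "If PEG-interferon or other immunomodulator therapies are used then the participant's outcome will be treated as a failure". Neither sentence names a period.

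**The concern.** The responder rule is what gets programmed, and for one variable of four it does not deliver the stated estimand. Someone who took an immunomodulator during dosing, stopped before follow-up and then held HBsAg below LLOQ would count as a success on that variable.

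Two comparisons would suffer. Actual-end HBsAg response and actual-end SVR should differ only through HBV DNA, but could differ because of the medication rule. Planned-end and actual-end HBsAg response could differ for completers although both use the same measurements.

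**Working it through.** The plan gives no figure for this endpoint, so there is none to reproduce. Its sample-size tables concern the primary endpoint and do not depend on this rule. The check compares the statements, then the analysis windows, then works through cases.

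**1. Periods covered by each statement**

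| Statement | Treatment period | Follow-up |
|---|---|---|
| Protocol 9.4.4 | yes (no limit stated) | yes |
| SAP 4.3.1.1 estimand | yes (no limit stated) | yes |
| SAP 4.2.2.1 primary rule | yes | yes |
| SAP 4.3.1.1 HBsAg, planned end | yes | yes |
| SAP 4.3.1.2 SVR, planned end | yes | yes |
| SAP 4.3.1.2 SVR, actual end | yes | yes |
| SAP 4.3.1.1 HBsAg, actual end | **no** | yes |

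**2. Do the windows explain the difference?** SAP 6.2.5 sets the actual-end windows from "X = Target study day of the last treatment dose". For a participant whose last dose is the Week 12 visit, X = 78:

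| Timepoint | Actual-end formula | With X = 78 | Planned-end window as printed |
|---|---|---|---|
| End of treatment | max(X−14, 1) to X+20 | 64–98 | 64–98 |
| Week 8 after | X+21 to X+76 | 99–154 | 99–154 |
| Week 16 after | X+77 to X+132 | 155–210 | 155–210 |
| Week 24 after | X+133 to X+188 | 211–266 | 211–266 |

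All four windows agree, as do the later target days (78+56 = 134, 78+112 = 190, 78+168 = 246). For these participants both HBsAg variables use the same values under 6.2.5, and the medication step is what can separate them. Nor do the windows exclude on-treatment time: the first opens 14 days before the last dose, while SAP 6.2.2 starts the off-treatment period 7 days after it.

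**3. Cases.** Take a completer with HBsAg and HBV DNA below LLOQ in every window, none missing:

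| Use on treatment | Use in follow-up | HBsAg actual, as written | The other three variables |
|---|---|---|---|
| no | no | Responder | Responder |
| no | yes | Non-Responder | Non-Responder |
| **yes** | **no** | **Responder** | **Non-Responder** |
| yes | yes | Non-Responder | Non-Responder |

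One case out of four differs, and only in the direction of more responders.

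**4. Weight of one such participant.** 1/20 = 5.0 percentage points; at the maximum enrolment, 1/24 = 4.2 points.

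**5. Early stoppers.** The rule does not define its follow-up period. If it means the scheduled 24 weeks after the planned 12, use between an early last dose and the planned end is also missed, although it falls inside that participant's actual-end windows. If it runs from the actual end, only use while still on treatment is missed.

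**The case against.** The best defence is that the narrower rule was intended. The SAP defines the variable as response "for 24 weeks after the actual end of GSK3228836 treatment without the use of PEG-interferon or other immunomodulator therapies", which can be read as requiring no use only in those 24 weeks, and the estimand sentence does not expressly say use at any time. This reading fails. The estimand sentence carries no limit, and actual-end SVR has the same anchor and windows yet its rule names both periods. If the narrow reading were right, the actual-end SVR rule would be the faulty one, and the two would still need reconciling.

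A second objection concerns intent. SAP 4.8 Table 1 lists only the ALT time-to-event change ("Now presenting 4 tables instead of one"), so this rule is not a declared departure. But Table 1 is not exhaustive: the categorical anti-HBsAg variable added in SAP 4.3.1.3 is absent from it as well. That stands, so Table 1's silence is weak evidence of a slip. The comparison with the parallel rules carries the point.

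Third, the matching of planned-end and actual-end data rests on the 6.2.5 windows. The planned-end variable is described as using Week 13 to Week 36, whereas its first window opens on Day 64. SAP 4.3.1.1 itself refers to 6.2.5 for the windows, so they are taken as operative here.

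Finally, the practical effect is slight. Protocol 6.8.2 prohibits "PEG-interferon or other immunomodulating therapies", a course continuing into follow-up is already caught, and the affected participant must also be below LLOQ in every window. The 5.0 points is the weight of one hypothetical participant, not an estimated effect. All of this stands and sets the severity; it does not remove the inconsistency.

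**Conclusion.** The concern holds. As written, the actual-end HBsAg rule conflicts with its own estimand, with protocol 9.4.4 and with the three parallel rules, and the documents give no reason for the difference. It is a minor point: a descriptive secondary percentage without a test, a prohibited class of therapy, and few or no cases expected. The primary endpoint is unaffected.

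The conclusion rests on reading the estimand sentence as covering use in any period, as the parallel rules do. The documents give no rate of immunomodulator use, so the number of affected participants is unknown.

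**What to change.** In SAP 4.3.1.1, under the actual end of treatment, replace the first step with the wording of the planned-end rule: "If participant took PEG-interferon or other immunomodulator therapies during 12 week treatment period or 24 week follow-up period then participant is Non-Responder". This makes all four rules the same and closes the early-stopper gap whichever way the follow-up period is counted. Then check that the Output and Programming Specification and the program apply it; the protocol and SAP do not show how the rule was coded.

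The cost is one line of SAP text and a program check. Protocol 6.8 already requires every medication taken during the study to be recorded with start and end dates, so nothing further has to be collected.
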